- Contraindications and precautions for use are in general the same as for PhA and type 1 DM (see. Section 5.1.4. Recommendations), and are defined by DM complications and comorbidities.
- Additional factors limiting PhA in case of type 2 DM: coronary artery disease (CAD), diseases of the respiratory system, joints and others.
- The CAD risk requires mandatory electrocardiography (ECG) (according to the indications - stress tests, etc.) before starting PhA study.

In patients with type 2 DM, receiving insulin or oral hypoglycemic agents stimulating the insulin secretion (and very rarely - other hypoglycemic agents) PhA can cause hypoglycemia.

Education and self-control are carried out with the assistance of the clinical psychologist should be in compliance with the principles provided in the Russian algorithms (6th edition, 2013, Chapter 7, Education of the patients with DM).

Observation period is 12 months. The objective is to reduce weight no less than 5% compared with the baseline in the first three months and then to maintain the positive dynamics in the next 9 months.

Weight reduction will help to improve the metabolism of carbohydrates and lipids as well as to reduce the risk of complications.

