5.1 Primary endpoint

Number (proportion) of patients in active and control group that achieved weight loss of at least 5% in comparison with baseline at 12 months of observation.

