12.1 Treatment response variables

Descriptive statistics for body weight (kg), body mass index (kg/m²), waist circumference (WC, cm) and waist to hip ratio (WHR), HbA1c%, fasting blood glucose (mmol/L), lipid profile (cholesterol, triglycerides, LDL, HDL) values together with absolute and relative (%) changes from baseline, as well as systolic and diastolic blood pressure (mmHg) values together with absolute changes, will be tabulated by visit for the FAS population. In addition, descriptive statistics for the above variables and their changes will be tabulated for visits corresponding to Weeks 12, 24, 36, 48, after the imputation of missing values using LOCF approach.

The primary endpoint - the number (proportion) of patients for whom body weight decreased by at least 5% compared to baseline values at 12 months of observation - will be analyzed in FAS (LOCF), additionally the primary endpoint analysis will be repeated in the Per Protocol Set (PP).

The number and proportion of patients with a decrease in body weight of at least 5% compared to the baseline values at 12 months of observation will be tabulated based on available measurements and based on imputed (LOCF) values in the FAS population. The results for the primary endpoint will also be presented by centers.

To compare proportions between groups, the main analysis of the primary endpoint will be carried out using logistic regression with the calculation of the odds ratio with 95% CI. In order to adjust for the potential confounding factors, potentially influencing factors such as age, gender, baseline value of the body mass index, the duration of the disease, baseline level of HbA1c will be included in the regression model.

As part of the sensitivity analysis, the primary endpoint will be analyzed without imputation of missing values using the GEE (Generalized Estimating Equations) method, taking into account the correlation of the repeated measurements at different visits for each patient.

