The model will include group, time (visit) and group*time interaction. In addition to group, time and interaction term, only significant influencing factors (age, gender, baseline body mass index, disease duration, baseline HbA1c) ($p < 0.1$) will be included in the model. A first order autoregressive covariance structure [AR (1)] will be used in the model. If convergence is not achieved, other covariance structures (Independent, unstructured covariance structure (Unstructured)) will be tested as possible alternatives. Differences between groups (active group - control group) will be assessed using interaction term group*time, calculating the adjusted means and corresponding 95% confidence intervals for the group*time interaction.

Secondary dichotomous variables - a decrease in body weight by at least 5% at 3, 6, 9 months of observation and at least 10% of the baseline values at 3, 6, 9, 12 months of observation will be analyzed in a similar manner.

Secondary dichotomous endpoints – a decrease of HbA1c level by at least 0.5% from baseline, achievement of HbA1c $\leq 7\%$ by 12 months of observation, a decrease in SBP and DBP by at least 5 mmHg at 3, 6, 9, 12 months of observation - will be analyzed using GEE with the imputation of missing values.

After the imputation of missing values, the endpoints representing the absolute and relative (%) changes in the quantitative variables for 3, 6, 9 and 12 months will be analyzed using the GEE method. The initial values of the relevant variable, age, sex, baseline body mass index, duration of the disease, and the initial value of HbA1c% will be used as factors and covariates. 95% confidence intervals for mean values of the parameters in both groups will be presented, as well as for the difference in the mean values between the compared groups adjusted for the influence of these factors.

In case of significant deviations from the normal distribution (verified using graphical methods), the logarithmic transformation or nonparametric Mann-Whitney U-test will be used as possible alternatives.

All data on primary and secondary endpoints will also be presented in the form of listings.

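### The GEE sensitivity analysis of the primary endpoint ties the group comparison to the group*time interaction and names no month-12 between-group contrast, odds ratio or confidence interval

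*SAP*

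**What the plan says.** SAP section 5.1 defines the primary endpoint as "Number (proportion) of patients in active and control group that achieved weight loss of at least 5% in comparison with baseline at 12 months". Section 12.1 says that "the main analysis of the primary endpoint will be carried out using logistic regression with the calculation of the odds ratio with 95% CI". That analysis uses the full analysis set (FAS) with last observation carried forward (LOCF) and is repeated in the per-protocol set.

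Section 12.1 then adds a sensitivity analysis in which "the primary endpoint will be analyzed without imputation of missing values using the GEE (Generalized Estimating Equations) method". On its terms: "The model will include group, time (visit) and group*time interaction". On the correlation: "A first order autoregressive covariance structure [AR (1)] will be used in the model". On the comparison of groups: "Differences between groups (active group - control group) will be assessed using interaction term group*time", and the same sentence continues with "calculating the adjusted means and corresponding 95% confidence intervals for the group*time interaction".

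Nothing else in section 12.1 says how a group difference is to be read from a GEE responder model. The entry for Table 4.1.3.3 in the list of tables names no contrast either.

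Protocol section 10 gives the programme's goal as "to reduce weight no less than 5% compared with the baseline in the first three months and then to maintain the positive dynamics" over the following nine months.

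**The concern.** A patient cannot have lost 5% of baseline weight at baseline, so only post-baseline visits inform the model. There the group*time term measures how the group effect differs between visits. It does not measure the size of the effect at any one visit. If the interaction carries the conclusion, a benefit reached by month 3 and held to month 12 gives a null result. A benefit present at month 3 and gone by month 12 can give a significant one.

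This matters because the analysis is the only inferential FAS analysis of the primary endpoint without imputation. The plan expects about 20% dropout in the active group and none in the control group, so LOCF falls mainly on the active group, and this analysis is the check on it. A null interaction could be misread as showing that the primary result is not robust, and a significant one as support for a benefit that no longer exists. If the choice between the interaction p-value and the month-12 means is left open, it can be made after the data are seen.

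**Working it through.** **The plan's own figure.** The only power figure is the 80% in SAP section 3, for a 5% weight change. It cannot be reproduced because no SD or responder rate is given. It would imply an SD of weight change of 8.34% with 80 v 30 patients, or 8.57% with 100 v 30. It does not bear on this point, and the SAP gives no figure for the GEE analysis.

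**Definitions.** Let p_A,t and p_C,t be the responder proportions in the active and control groups at month t, for t = 3, 6, 9, 12, the assessment times common to both groups. Let d_t = logit(p_A,t) − logit(p_C,t), the log odds ratio at visit t.

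- Interaction test (3 df): d_3 = d_6 = d_9 = d_12.
- Month-12 contrast (1 df): d_12 = 0.

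Both come from the same fitted model. With month 12 as the reference visit, d_12 is the group coefficient.

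**By hand, with assumed rates.**

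- Constant benefit, 50% v 15% at every visit: odds ratio = (0.50/0.50)/(0.15/0.85) = 5.67 each time. The differences between visits are zero, so the interaction is exactly null despite the large effect.
- Lost benefit, active 60/50/35/15% v control 15%: odds ratios 8.50, 5.67, 3.05 and 1.00. The interaction is large, yet the groups do not differ at month 12.

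The first result is algebra: it holds for any constant odds ratio.

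**By simulation.** From the documents: 100 × (1 − 0.20) = 80 active and 30 control patients, four visits, alpha 0.05 (taken as two-sided). Assumed: the responder rates, a latent AR(1) correlation of 0.7, and complete data. The model was a saturated group-by-visit logistic model with robust covariance, unadjusted for covariates. There were 4,000 runs per scenario; runs with an empty control cell were dropped.

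| Active v control | Interaction, 3 df | Month-12 contrast |
|---|---|---|
| Constant 50% v 10% | 5.7% | 99.1% |
| Constant 50% v 15% | 5.1% | 94.3% |
| Constant 40% v 10% | 5.9% | 89.5% |
| Constant 50% v 20% | 5.5% | 84.2% |
| Constant 60% v 20% | 5.4% | 97.5% |
| Lost: 60/50/35/15% v 15% | 70.0% | 2.8% |
| Lost: 70/50/30/20% v 20% | 85.1% | 3.3% |
| No effect: 20% v 20% | 6.3% | 4.2% |

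Reading the single month-12 v month-3 interaction coefficient (d_12 − d_3) does not help. It rejects in 1.8–5.7% of runs under constant benefit, and in 78.8% and 88.3% under the two lost-benefit patterns.

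**Cross-check with the SAP's AR(1) structure.** GEE fits, 59 usable datasets per scenario: constant 50% v 15%, interaction 5% and month-12 contrast 100%; the first lost-benefit pattern, 61% and 0%.

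**Limits.** Runs dropped in the two scenarios with a 10% control rate were 594 and 516 of 4,000 (14.9% and 12.9%), so those two rows are the least certain.

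**The case against.** The strongest reply is that the sentence must be read whole. It defines a signed difference, active minus control, and asks for adjusted group*time means with 95% CIs. An omnibus interaction test has no sign and no such means. The text may therefore intend visit-by-visit comparisons, including month 12, and the SAP nowhere prescribes the 3-df test simulated here. This stands as a plausible reading, and a reader who infers that the GEE cannot address month 12 goes further than the documents allow. It does not settle the matter: a mean and interval for each group at each visit are not a between-group difference with its own interval. For the quantitative endpoints, the same section does ask for an interval for the adjusted difference between groups.

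Second, the primary inference is safe. The FAS/LOCF logistic regression and its per-protocol repeat address month 12 directly, and month-12 proportions on available data are tabulated. This stands in full.

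Third, a reader might infer that all secondary responder endpoints share the problem. The documents do not support that. The 5% and 10% weight-loss endpoints are to follow the primary endpoint's approach, whose main analysis is logistic regression. SAP section 16 lists only the HbA1c and blood pressure responders as moved from visit-specific logistic regression to GEE. The ambiguity may reach those, since no other contrast is stated for them, and it may reach any GEE run on the weight-loss endpoints.

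Fourth, the goal in Protocol section 10 is a programme aim, not a statistical assumption, and could mean continuing loss. This is fair: the interaction is null only if the odds ratio is constant across visits. The goal makes a roughly constant benefit plausible, not certain.

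**Conclusion.** The point holds as a gap in specification. The SAP names the interaction as the basis for the group comparison in the GEE sensitivity analysis and does not name the month-12 contrast that the endpoint requires. Taken as a test, the interaction answers a different question. Its null value under a constant odds ratio needs no assumption. The size of the loss does: the simulated rates rest on assumed responder proportions, correlation and complete data, and they show how far the two criteria can diverge, not what this trial will conclude.

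The consequence is confined to the GEE sensitivity analysis and to any responder endpoint judged by the same rule. It should be corrected before analysis, but it does not put the primary result in doubt.

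**What to change.** In SAP section 12.1, replace the sentence on assessing group differences with a statement on these lines: the result of the GEE sensitivity analysis is the active v control contrast at week 48, given as an odds ratio with 95% CI, from the model with group, visit and group*visit. Wherever another responder endpoint is analysed by GEE, use the corresponding visit-specific contrast (weeks 12, 24, 36 or 48, as the endpoint requires). Keep the adjusted group-by-visit means as supporting output, and report the interaction test only as a description of change over time. Name the contrast in the title of Table 4.1.3.3.

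The cost is a few lines of text. The model, data and visits stay the same; only the reported contrast changes.

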12.3 Database management and quality control

Novartis staff, or CRO working on behalf of Novartis, review the data entered into the eCRF by investigational staff for completeness and accuracy and instruct the site personnel to make any required corrections or additions.

Queries are sent to the investigational site using an electronic data query. Designated investigator site staff is required to respond to the query and confirm or correct the data.

Concomitant medications entered into the database will be coded using the World Health Organization (WHO) Drug Reference List, which employs the Anatomical Therapeutic Chemical classification system.

Medical history and AEs will be coded using the Medical Dictionary for Regulatory Activities (MedDRA) terminology.

13 Data analysis

Descriptive statistics will be applied in the study to describe the sample size of the patients at baseline and at follow-up visits, demographic data recorded during the examination of the study parameters, as well as their changes.

The choice of parametric or non-parametric criteria for testing statistical hypotheses will be determined on the basis of the Kolmogorov-Smirnov criteria (conclusion of the presence or absence of statistically significant differences between the distribution of the respective parameter and the normal one), as well as with the graphical methods.

AE data will be presented as an absolute number and as the proportion of the patients with any AE, according to the organ systems and specific AE with corresponding 95% confidence intervals (CI). The association between therapy duration and AE (SAE) risk will be analyzed on the basis of the proportional-hazards regression model of the survival analysis. Age, sex, BMI, disease duration, baseline HbA1c, will be taken into account in the model for the control of potential confounding factors. Secondary indicators will be analyzed the same way.

The primary analysis of the proportion of the patients with response on the treatment will be performed using multivariate logistic regression and calculating odds ratios with

corresponding 95% CI. To control the potential confounding factors, age, sex, BMI, disease duration, the baseline values of HbA1c will be taken into account in the regression model.

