- 1) Structured modified diet change;
- 2) Balanced and personalized physical exercises;
- 3) Cognitive behavioral support;
- 4) Intensive interactive medical assistance;
- 5) Group education.

The total duration of the study for each patient is 12 months (1 month is equal to 4 weeks or 28 days). Patients from active group will be monitored intensively during the first three months (weekly, with allowed visit window of +/- 1 day) and then will continue to participate in the study for the remaining 9 months. After the first 13 weeks, monthly (+/- 3 days) assessments of weight and health status of patients from the active group will be performed. Key laboratory parameters will be measured and the physician will make a decision on whether the diabetes therapy should be adjusted as the patient's weight is reduced.

3 Sample size determination

The primary objective of this study is to assess the change of weight from baseline, in patients with T2DM at 12 months in comparison to the change in weight from baseline in the parallel cohort. Sample size was calculated based on weight changes observed in Why Wait study conducted at the Joslin center. The average weight loss observed at the end of 12 months was 8%. Given that baseline criteria and translation of the program can be different in its implementation in Russia, we have assumed an achievable change in weight as 5%. Significant reduction of body weight in the control group is not anticipated. The sample size (with the possible dropout of 20%) of 100 patients in active group and 30 patients in parallel cohort is sufficient to provide 80% power to detect a significant difference (significance level is $\alpha=0.05$) between values in the two groups.

4 Randomization and blinding

Not applicable.

5 Efficacy assessment

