5.2 Secondary endpoints

- Body weight decrease expressed in percents and in absolute values in comparison with baseline at 3, 6, 9, 12 months of observation;
- Number (proportion) of patients achieved weight loss of at least 5% in comparison with baseline at 3, 6, 9 months of observation;
- Number (proportion) of patients achieved weight loss of at least 10% in comparison with baseline at 3, 6, 9, 12 months of observation;
- Changes of HbA1c and FPG levels expressed in percents and in absolute values;
- Number (proportion) of patients achieved decrease of HbA1c by at least 0.5% in comparison with baseline;
- Number (proportion) of patients achieved HbA1c $\leq 7\%$ at 12 months of observation;
- Blood pressure changes in absolute values in comparison with baseline;
- Number (proportion) of patients achieved decreasing of systolic and diastolic blood pressure levels by at least 5 mmHg in comparison with baseline;
- Changes of lipid profile (cholesterol, triglycerides, LDL, HDL) expressed in percents and in absolute values in comparison with baseline;
- Changes of waist circumference, waist-to-hip ratio;
- Changes of BMI;
- Assessment of changes by Hypoglycemia Perspectives Questionnaire for active group patients, as well as by perceived exertion rate with Borg scale.

6 Patients enrolled in the study

The study planned to include 130 patients with type 2 diabetes and obesity. In the active group, it was planned to recruit 100 patients, who will actively participate in lifestyle correction program; the control group will consist of 30 patients with T2DM, matching the active group patients by main parameters, who will to be managed in accordance with routine clinical practice for T2DM patients. The control group should be comparable to the active group with regard to the core baseline parameters.

When forming the control group, the following criteria should be taken into account (inclusion criteria in the study): BMI (<30 ; ≥ 30) and baseline HbA1c (<7.5 ; ≥ 7.5). The decision about inclusion of a patient in the active or control group is left at the discretion of the treating physician.

Dropout of 20% from initially enrolled population was considered by the study design. The patient's dropout from the study is defined as three consecutively missed classes within the first 12 weeks of observation in the active group. No dropout in the control group is assumed.

Patients are distributed between two sites participating in the study.

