The scale of individual perception of physical activity (the Borg scale) was filled on Visit 1 and at the end of the program in the active group. The score on the scale will be presented using descriptive statistics as the number and proportion of patients for each category. Changes will be presented as cross-tabulation of estimates at the beginning and after the program.

The questionnaire for hypoglycemia evaluation was filled on Visits 1, 24 and 48 weeks of observation. For each patient, the result for subscales 4, 5, 6, 7, 8, 9 will be calculated as the mean value of answers to subscale questions. The results for all subscales and changes from baseline will be presented descriptively by groups and visits.

14 Interim analysis

Not planned.

15 Presentation of results

Statistical analysis will be performed using IBM® SPSS® Statistics Version 19.0 or later. All results will be presented in the form of tables, listings and figures.

16 Changes in the statistical analysis plan

The analysis of the quantitative efficacy endpoints at each individual assessment visit using ANCOVA was replaced with an analysis based on a similar model, which takes into account the correlation between the repeated measurements, using the GEE method (Generalized Estimating Equations).

Secondary dichotomous endpoints - a decrease of HbA1c level by at least 0.5% from baseline, achievement of HbA1c $\leq 7\%$ by 12 months of observation, a decrease in SBP and DBP by at least 5 mmHg at 3, 6, 9, 12 months of observation - will also be analyzed using GEE (logistic regression of repeated changes) instead of logistic regression for individual evaluation visits.

17 References

1. ICH (1998). International Conference on Harmonization. Guideline E9 on Statistical Principles for Clinical Trials.

18 List of results

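### For the secondary quantitative endpoints, SAP 12.1 lets a normality plot replace the covariate-adjusted GEE with an unadjusted Mann-Whitney test or a log of an unnamed quantity, on a trigger that differs from Protocol 13

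*SAP*

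**What the plan says.** SAP 12.1 analyses absolute and percent changes at 3, 6, 9 and 12 months by GEE. The covariates are the variable's own baseline, age, sex, baseline BMI, disease duration and baseline HbA1c. It promises 95% confidence intervals, including one "for the difference in the mean values between the compared groups adjusted for the influence of these factors". The next paragraph says that if plots show significant departures from normality, "the logarithmic transformation or nonparametric Mann-Whitney U-test will be used as possible alternatives".

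SAP section 16 explains that GEE replaced visit-by-visit ANCOVA with a similar model "which takes into account the correlation between the repeated measurements".

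Protocol section 13 has a different gate: "The choice of parametric or non-parametric criteria for testing statistical hypotheses will be determined on the basis of the Kolmogorov-Smirnov criteria", together with graphical methods. In its adverse-event paragraph it names five covariates that "will be taken into account in the model for the control of potential confounding factors", and ends: "Secondary indicators will be analyzed the same way".

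The study is not randomised. SAP section 6 leaves the choice of group to the treating physician and names two matching cuts, BMI at 30 and HbA1c at 7.5. It adds a general aim: "The control group should be comparable to the active group with regard to the core baseline parameters".

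**The concern.** The fallback is not a variant of the planned analysis. It changes what is estimated and whether confounders are controlled, and it is triggered by looking at the outcome data. In a physician-allocated comparison, covariate adjustment is the SAP's main analytic protection for these endpoints, so it should not depend on the shape of a plot. The fallback is also not fully executable: two analysts following the text could log different quantities, or choose different alternatives, for the same endpoint. What is at stake is the reported result for weight change, BMI, waist, waist-to-hip ratio, HbA1c, fasting glucose, blood pressure and lipids.

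**Working it through.** **1. Planned model and fallback side by side.** No figure in the plan attaches to the fallback, so there is none to reproduce.

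| | Planned GEE | Mann-Whitney on changes | Log transformation |
|---|---|---|---|
| Covariates | six | none (own baseline only by subtraction) | not stated |
| Repeated visits | modelled | one visit at a time | not stated |
| Adjusted mean difference with CI | yes | no | only on another scale |
| Quantity analysed | change, % change | change, % change | not stated |

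**2. Is the log defined?** SAP section 3 says: "Significant reduction of body weight in the control group is not anticipated". Assume a control mean change of 0 and a symmetric distribution: about 50% of control changes cannot be logged under either sign convention. For the active group take the plan's assumed 5% loss. The SD is not given. The value implied by 80% power with 100 v 30 is 5 / [(1.960 + 0.842) × √(1/30 + 1/100)] = 8.6 points, so use 5 to 8.6. The share of active changes at or below zero is Φ(5/5) = 84% to Φ(5/8.6) = 72%. With loss counted as positive it is 16% to 28%. The log works only on values or ratios, which the SAP does not say.

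**3. Does the choice of analysis matter?** All inputs here are assumptions except the group sizes: 80 active (100 less the planned 20% dropout) v 30 controls. Assume no programme effect, a baseline difference of d = 0.3 or 0.5 SD, and baseline to follow-up correlation r = 0.5 or 0.7.

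- If follow-up depends on baseline alone, the unadjusted change differs by −(1−r)d and the adjusted difference is 0.
- If the groups differ stably, the unadjusted change differs by 0 and the adjusted difference is +(1−r)d.

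With k = √(1/80 + 1/30) = 0.2141, the standardised shifts are:

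- Mann-Whitney, baseline alone: n = √(3/π) × (1−r)d / [√(2(1−r)) × k]
- Adjusted model, stable difference: n = (1−r)d / [√(1−r²) × k]

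The two-sided 5% false-positive rate is Φ(n − 1.96) + Φ(−n − 1.96). Simulated values (4,000 runs per cell, AR(1) GEE, month-12 contrast) are in brackets; for the GEE they are uncorrected / small-sample corrected.

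| d | r | (1−r)d | Mann-Whitney, baseline alone | Adjusted, stable difference |
|---|---|---|---|---|
| 0.3 | 0.5 | 0.15 | 10.5% (9.4%) | 12.8% (14.3 / 11.8%) |
| 0.5 | 0.5 | 0.25 | 20.7% (19.2%) | 27.1% (27.8 / 23.5%) |
| 0.3 | 0.7 | 0.09 | 8.3% (8.5%) | 9.1% (11.2 / 8.8%) |
| 0.5 | 0.7 | 0.15 | 14.3% (14.0%) | 16.5% (17.3 / 14.2%) |

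In each mechanism the other method stays near nominal: the GEE at 5.6–6.5% uncorrected (4.1–4.9% corrected) under baseline alone, Mann-Whitney at 4.6–5.1% under a stable difference. At correlation 0.9–0.95 with baseline alone they hardly differ (Mann-Whitney 6.0–7.7%, GEE 6.1–7.7%). In simulated skewed data (r = 0.5–0.7), the two disagreed on significance in 5.9–7.1% of trials without imbalance and 8.0–31.0% with it.

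**4. Check-then-switch.** A single-visit stand-in was simulated: ANCOVA with robust errors, Lilliefors test at 5% on the residuals, switch to Mann-Whitney if it fires, 80 or 100 v 30, 1,500 runs. On normal data with imbalance under baseline alone, the rule gives 4.9–5.7%. On lognormal data (log-SD 0.3) without imbalance it gives 4.5–4.7%. With imbalance of 0.3–0.5 SD it gives 6.1–13.9% under baseline alone (always adjusted: 4.6–5.1%) and 7.5–18.3% under a stable difference (always adjusted: 9.3–30.4%).

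**5. Does the trigger matter?** On simulated skewed data (n = 110, log-SD 0.2–0.5), plain Kolmogorov-Smirnov at 5% fires in 0–7.7% of trials for absolute change, and its Lilliefors form in 5.7–58.7%. For percent change the figures are 0.4–46.9% and 21.8–95.6%. A plot without a threshold has no rate to compute.

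**The case against.** The strongest reply is that harm is not shown. A reader might infer that the Mann-Whitney route inflates false positives and the adjusted GEE is safe. The documents do not support that. The table shows equal spurious differences of opposite sign, and nothing in either document says which mechanism holds. Where groups differ stably, switching lowers the error rate. This stands, and it limits the point to pre-specification and keeping the planned estimand.

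Other points that stand:

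- The wording is permissive, so a switch is allowed rather than certain. The open discretion is itself the gap.
- A reader might infer that the analyst may take the most favourable of the three results. SAP 12.1 does not permit that; it only fails to say which applies.
- A reader might infer that Protocol 13 requires the five covariates for every secondary endpoint. The sentence follows the adverse-event model and its reach is unclear, so the point does not rest on it.
- Both documents use plots. The difference is the missing Kolmogorov-Smirnov criterion, which the change list in SAP section 16 does not mention.
- Change scores already use the endpoint's own baseline by subtraction, so that adjustment is weakened rather than lost. The other five covariates are lost.

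None of this answers the main gap: the fallback cannot deliver the adjusted difference that SAP 12.1 promises, and its log option is undefined as written.

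**Conclusion.** The point holds for the secondary quantitative endpoints only. The primary endpoint is a binary response analysed by logistic regression, and the normality fallback does not reach it.

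Three things follow from the text without assumptions: the fallback can remove the planned adjustment, repeated-measures structure and estimand; the logged quantity and the choice between alternatives are unspecified; and the two documents state different triggers. The size of any effect on conclusions rests on assumed imbalance, correlation and skewness. It can be negligible (high correlation, or no imbalance) or a spurious difference of up to 0.25 SD, in either direction. The case for change is that it keeps the SAP's own estimand and removes a data-driven switch, not that it has a proven lower error rate. Severity: minor to moderate.

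**What to change.** In SAP 12.1:

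1. Report the covariate-adjusted GEE with robust standard errors for every quantitative endpoint, whatever the normality check shows. Its robust standard errors do not rely on normal outcomes.
2. Pre-specify one additional analysis for skewed endpoints: the same GEE on log(value/baseline), with log baseline in place of the baseline value and the other covariates unchanged, reported as an adjusted ratio of geometric means. All 12 variables (weight, BMI, waist, waist-to-hip ratio, HbA1c, fasting glucose, SBP, DBP and four lipids) are positive, so it is always defined.
3. Label any Mann-Whitney result supportive and unadjusted, never a replacement.
4. State one trigger in both SAP 12.1 and Protocol 13 (what is checked, pooled or by group, which test and level), used only to add the log-ratio result.

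Cost: a few SAP sentences and one in Protocol 13, with no new data. Some endpoints gain an extra scale; blood pressure, for example, is planned as absolute change only. Uncorrected robust errors are slightly liberal with 30 controls (6.1–6.5% without imbalance, against 4.7–4.9% with a small-sample correction). In the balanced setting simulated (true effect 0.5 SD of the change, correlation 0.5–0.9), power was 62.4–73.1% for the corrected GEE and 60.8–61.9% for Mann-Whitney, so no loss of power appeared there.
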